## Protocol Synopsis

### Low-level light therapy (LLLT) with near infrared light emitting diodes in patients with moderate traumatic brain injury

Trial Population	Males and females 18 years and older admitted to the Emergency Department (ED) or Trauma Service with a head injury requiring hospital admission as either an inpatient or for observation.
Investigational Product	Custom designed Photomedex helmet with LED cluster heads emitting near infrared light.
Control	Randomized subjects assigned to the placebo procedure (non-activated Photomedex helmet)
Trial Design	Double-blinded placebo controlled study
Primary Objective	Safety and feasibility of using the Photomedex helmet for LLLT and quantify the response to LLLT using magnetic resonance imaging and clinical outcome measures.
Number of Subjects	Up to 90 subjects at Massachusetts General Hospital will be enrolled into the trial.
Key Inclusion Criteria	

• At least 18 years old;

• Injury within 72 hours at the time of consent;

• Head injury requiring hospital admission;

• A Glasgow Coma Scale (GCS) score of 9-12 or 13-15 with abnormal imaging.

Key Exclusion Criteria	

• Need for emergency neurosurgical intervention (including placement of intracranial pressure monitoring devices or drainage catheters);

• Hemodynamic instability as determined by the clinician;

• History of any of the following: (i) brain tumor; (ii) prior TBI occurring within the past year and requiring hospital admission; (iii) a new diagnosis within the past year of either stroke or epilepsy; (iv) an established diagnosis of any of the following neurodegenerative diseases: Alzheimer's, Picks, Parkinson's, Lewy body dementia,

	
Huntington's, amyotrophic lateral sclerosis, spinocerebellar ataxia, vascular dementia, HIV-associated dementia, dementia due to metabolic causes (Addison, Cushing, hypothyroidism, renal failure, porphyrias, Wilson, mitochondrial diseases, Wernicke-Korsakoff syndrome, and dementia of unknown etiology.
 
 
• Pregnancy (all women of child-bearing age will need to have a negative pregnancy test prior to the start of the interventional portion of the study);
 
• Electrical implants such as cardiac pacemakers or perfusion pumps;
 
• Ferromagnetic implants such as aneurysm clips, surgical clips, prostheses, artificial hearts, valves with steel parts, metal fragments, shrapnel, tattoos near the eye, or steel implants, or any other contraindications to MRI.
 
• Clinical determination that subject cannot undergo MRI
 
• Breastfeeding
 
• Unstable cervical fractures
 
• Scalp lacerations or surgical wounds severe enough to preclude safe application of device
 
• Unreliable to follow up
 

Primary Endpoint	Safety and feasibility of using the Photomedex helmet for LLLT and will be based on the number of subjects who successfully complete the study without adverse events significantly related to application of the device.
Secondary Endpoint	The secondary endpoint will be quantification of the subject response to LLLT using MRI and clinical outcome measures.
Regulatory Status	
This trial will be conducted as a Non-Significant Risk device trial in accordance with both the Food and Drug Administration's regulations and guidelines.
 
 21 CFR 812.2(b)(1)   U.S. Department of Health and Human Services, Food and Drug Administration, Center for Device and Radiological Health (January 2006). Information Sheet Guidance For IRBs, Clinical Investigators, and Sponsors: Significant Risk and Non-significant Risk Medical Device Studies.

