**3. Subject Selection**

In this study, we propose to conduct a double-blinded placebo-controlled trial and enroll 90 subjects with moderate TBI to confirm the safety and feasibility to: 1) use the Photomedex Helmet to deliver low-level laser light through the scalp/skull and 2) track the response of delivery through MRI and clinical examinations.

Only patients presenting to the Emergency Department (ED) and/or admitted to the Trauma Service at Massachusetts General Hospital (MGH) will be considered. The following are the inclusion/exclusion criteria for the study.

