## **9. Statistical Methods**

In this pilot study, the study size is limited by number of recruitable patients admitted to MGH emergency department. Based on prior-year admission records, the itemized inclusion/exclusion criteria, and an assumed 80% consent rate, we estimate an average enrollment of 1 patient per week.

The sufficiency of these enrollments toward powering the primary hypothesis (DTI outcome measure) is presented below. These calculations require an assumption of the acute LLLT therapeutic effect size, which is unknown and cannot reasonably be estimated from either the preclinical data or the clinical stroke studies. Our analysis is based on an assumed effect size of 25%.

The coefficient of variation for fractional anisotropy (FA) is based on data from a cohort of 12 mild to moderate TBI patients scanned using quantitative MRI [30]. For this cohort, FA was measured in 16 regions of the brain. The coefficient of variation (CV), defined as the ratio of mean to the standard deviation, was 53.45%. However, this study included mild to moderate. With the more narrow inclusion of moderate TBI, we estimate a FA CV of 40% (based on clinical and research experience of the investigators, and knowing that the CV for healthy volunteers is 25%). The required sample size for detecting changes in FA associated with acute LLLT [31] is then 82 (41 patients in each group). We note that other diffusion parameters (mean diffusivity, axial diffusivity, and radial diffusivity) featured much lower CV, and would be sufficiently powered with this sample size.

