Light Therapy for Moderate Traumatic Brain Injury

NCT02233413

Statistical Analysis

6.26.20

Statistical Analysis

All statistical analyses were performed using R Language for Statistical Computing (version 3.6.0). Differences and relations were considered statistically significant at $p < 0.05$. All results are presented as mean + standard deviation (S.D.) unless noted otherwise. Baseline differences across groups were compared via using one-way ANOVA for continuous variables (e.g., Age, RPQ scores) and via Chi-Square test for categorical variables. To test neuroreactivity of LLLT via its effect on the diffusion tensor parameters, we used a linear mixed effect (LME) model with treatment (light therapy vs. sham) and time point (acute, early sub-acute, late sub-acute) as fixed effects, and tract and time point nested within each patient as random effects. All patients with at least one MRI were included in this analysis. Conformity of the data to statistical assumptions were checked by investigating QQ plots of the data. LME models, which are akin to multiple regression models that can account for correlations due to repeated measures, have several advantages in this context. LME modeling allowed us to pool all our data --- i.e., across treatment groups and three time points, as well as across all 18 tracts --- to examine relationships robustly. Moreover, because the LME model allows partially repeated measures, it can accommodate data from subjects with missing timepoints (e.g., missing MRI sequences). In addition, the LME model treats each timepoint as a separate variable. Therefore, any baseline difference in DTI parameters across the LLLT and sham groups did not confound the overall analysis enabling one to robustly identify differences in DTI parameters across the treatment groups while explicitly accounting for repeated measurements, within-tract and within-subject correlations, and missing time points.

A similar LME model (treatment group and time point as fixed effects, and patient as a random effect) was used to test for the effect of LLLT on clinical symptoms). The p values for the fixed effects in the LME model were calculated using type III analysis of variance table with Satterthwaite's degrees of freedom method.

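### The synopsis makes a safety and feasibility count the primary endpoint, Section 9 calls DTI the primary hypothesis, and neither Section 9 nor the SAP analyses the count

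*Protocol*

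**What the plan says.** The Protocol Synopsis has the only headed endpoint hierarchy in the two documents. Its Primary Endpoint row names safety and feasibility of the helmet and says that this "will be based on the number of subjects who successfully complete the study without adverse events significantly related to application of the device". Its Secondary Endpoint row reads: "The secondary endpoint will be quantification of the subject response to LLLT using MRI and clinical outcome measures".

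Other places describe the aim more broadly:

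- The synopsis Primary Objective combines both: "Safety and feasibility of using the Photomedex helmet for LLLT and quantify the response to LLLT using magnetic resonance imaging and clinical outcome measures".
- Section 2 (Specific Aims) likewise joins feasibility with quantifying response by imaging and clinical measures, and its hypothesis covers both.
- Section 3 plans to "enroll 90 subjects with moderate TBI to confirm the safety and feasibility to" do two things: deliver the light, and track the response by MRI and clinical examination.

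Section 9 (Statistical Methods) takes a different line: "The sufficiency of these enrollments toward powering the primary hypothesis (DTI outcome measure) is presented below". The rest of that section is an accrual rate and a sample size for FA.

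The SAP names no primary endpoint. After baseline comparisons it says: "To test neuroreactivity of LLLT via its effect on the diffusion tensor parameters, we used a linear mixed effect (LME) model". A similar model "was used to test for the effect of LLLT on clinical symptoms". The only analysis set it states belongs to the diffusion model: "All patients with at least one MRI were included in this analysis".

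**The concern.** DTI is an MRI measure, so one outcome is secondary in the synopsis and primary in Section 9. The outcome that the synopsis calls primary then disappears from the statistical plan. Section 1.3 presents the study as a pilot to assess feasibility, so the unanalysed endpoint is the result the pilot was set up to deliver.

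Two things are at stake. First, a DTI p-value could be read as the trial's primary result on the strength of Section 9, although the synopsis ranks it second. Second, the safety and feasibility conclusion could be stated in words alone, with no denominator, no interval and no fixed rule for who counts as a success.

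**Working it through.** **1. What the sample size belongs to.** Inputs from Section 9: assumed effect 25%, FA coefficient of variation 40%. Section 9 gives no alpha or power. Two-sided 0.05 and 80% are assumed here, which the rule-of-thumb factor of 16 implies.

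- n per arm = 16 × CV² / (proportional change)² = 16 × 0.40² / 0.25² = 2.56 / 0.0625 = 40.96, rounded up to 41.
- Total = 2 × 41 = 82, which is the protocol's figure.
- Power by the normal approximation is 80.8% at 41 per arm and 84.2% at 45 per arm (90 split 1:1).

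No adverse event or completion rate enters. The sample size belongs wholly to an outcome that the synopsis calls secondary.

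**2. The statements side by side.**

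| Place | Status of safety/feasibility | Status of MRI/DTI |
|---|---|---|
| Synopsis, endpoint rows | Primary | Secondary |
| Synopsis, Primary Objective | In the primary objective | In the primary objective |
| Section 2 | In the aim | In the aim |
| Section 3 | To be confirmed | Tracking response by MRI is item 2 of what is to be confirmed |
| Section 9 | Not mentioned | Primary hypothesis; basis of the 82 |
| SAP | Not mentioned | Modelled; no rank given |

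The three merged statements fit either ranking, so they do not settle the conflict between the endpoint rows and Section 9.

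**3. Is the count analysed anywhere?** The SAP has three sets of analyses: baseline tests (ANOVA and Chi-Square), the diffusion mixed model and the symptom mixed model. The Chi-Square test is for baseline differences. Adverse events, completion, safety and feasibility do not appear. Sections 10 and 12.1 describe review by the investigator, the research monitor and the DSMB. That is oversight during the trial, and it sets no denominator, estimate, interval or by-arm table for the endpoint. Result: none of the three sets addresses the primary endpoint.

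**4. Can the count be formed uniquely from the text?** Not yet.

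- Completion is not tied to a last required contact. Section 7.3 has visits to 6 months and a call at 12 months.
- Completion is not tied to a number of helmet applications. Section 7.1 gives only a maximum of 3, while Section 11.1 gives a minimum of 2 and a maximum of 3. The two sections must be reconciled.
- The status of subjects withdrawn under the GCS rule in Section 7 is not stated.
- The degree of relatedness to the device that counts against a subject is not defined.
- No denominator is given. Application follows randomisation and waits on the clinician (Sections 7 and 7.1), so the randomised set and the set with an application can differ. The at-least-one-MRI set would leave out randomised subjects who were never scanned.

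**5. What an interval would add (illustration; counts assumed).** With 45 in an arm, 40 successes give 88.9% with an exact 95% CI of 75.9% to 96.3%. Zero device-related events in 45 give a two-sided exact 95% upper limit of 1 − 0.025^(1/45) = 7.9%. A bare count would not show that uncertainty. The finding does not depend on these figures.

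**The case against.** The best defence is that this is a pilot, that the synopsis hierarchy is clear under its own headings, and that the endpoint already names its summary: a number of subjects. A descriptive count can be enough for a pilot. Section 9 says hypothesis and not endpoint, and the objective and aims mix both strands, so the clash may be loose wording.

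Part of this stands. A reader might infer that nobody can tell which endpoint is primary. The documents do not support that, because the synopsis endpoint rows are explicit and are the only headed hierarchy. A reader might also infer that safety was not assessed. That is not supported either: adverse event assessment is scheduled in the Section 7 table, and Section 12.1 sets up DSMB and monitor review. Section 3 should not be cited as backing safety alone, since its second item is tracking response by MRI and clinical examination. Nor are the SAP's only p-values on secondary outcomes, because the baseline tests also give p-values.

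The defence does not reach the core. Even a descriptive primary endpoint needs a denominator, definitions and a measure of precision, and neither Section 9 nor the SAP gives them. No text explains why Section 9 ranks DTI differently from the synopsis.

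**Conclusion.** The plan is wrong as written on two linked points. The synopsis and Section 9 contradict each other on what is primary, and the endpoint that the synopsis declares primary has no planned analysis. In size: none of the SAP's three sets of analyses addresses it, both treatment-effect models concern outcomes that the synopsis ranks secondary, and the only sample size (82) rests on FA. This follows from the text. The only assumptions are the alpha and power used to reproduce 82 and the illustrative counts, and the conclusion does not rest on either.

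Two stronger readings should be resisted. One is that the sponsor switched outcomes. The documents show an unreconciled discrepancy and do not show when or why it arose. The other is that the sponsor may now settle the matter by naming DTI as primary. The SAP is written in the past tense, as an account of analyses already performed, so that choice would be made after the results could be known.

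**What to change.** 1. **Keep the synopsis hierarchy.** In Section 9, describe FA/DTI as the secondary outcome on which the sample size is based. Disclose the discrepancy between the synopsis and Section 9 in a dated note, and report diffusion and symptom results as secondary. The only exception is if dated records from before unblinding and analysis show that DTI was the declared primary.

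2. **Add a dated SAP addendum, labelled not pre-specified.**
   - Report the synopsis count by arm over all randomised subjects.
   - Report device-related adverse events, and any adverse event or serious adverse event, over all subjects with at least one helmet application, active or sham.
   - Give an exact 95% CI per arm and the between-arm difference with a 95% CI, as an estimate and not a powered test.
   - State that the at-least-one-MRI set is not used for this endpoint.

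3. **Define the two terms in that addendum.** For completion: the last required contact, the status of subjects withdrawn under the GCS rule, and helmet applications once Sections 7.1 and 11.1 are reconciled. For relatedness: what counts as significantly related to the device. The wording in Section 12.1 about events possibly or definitely related to participation is a trigger for forwarding reports. It is not a causality scale and should not be borrowed as the definition.

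**Cost.** A wording change in Section 9, a dated note, and an addendum with one or two tables. The data should come from the case report forms in REDCap (Sections 12.1 and 12.2) and the scheduled adverse event assessments. The documents do not say whether the forms record applications per subject, so this needs checking. The downside is that DTI p-values are presented as secondary and the added analysis is retrospective.

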## 7. **Research Design and Methods**

A member of the study staff familiar with the subject population will evaluate eligibility based on the approved inclusion/exclusion criteria, using patient charts. If a subject is eligible a physician on the study staff will approach the subject and/or surrogate for informed consent (please see consent procedures for more details). Demographic and clinical data will be collected during the acute hospitalization in accordance with the common data elements proposed by the TBI Common Data Element Project [29]. A drop point for deterioration for

withdrawing a subject will be a change in the GCS of greater than 2 from the previous exam.

After informed consent has been obtained, the subject will be randomized. All subjects will undergo either treatment or sham (placebo) procedures. In the sham procedure, the helmet will be placed on the patient but the LEDs will not be activated. The randomization will be set up so subjects are assigned sequentially into one of 9 groups with 10 subjects in each group. Within each group, the subject will be assigned randomly to either treatment or sham with an allocation ratio of 1:1. Once the first 10 subjects have been enrolled and have finished treatment (or sham) a DSMB (see detailed description under data safety and monitoring) will go over all of the safety data presented and make a recommendation on the continuation of the study. Subsequent DSMB meetings will take place once per year

If the subject is admitted to the ICU, he/she, will be treated according to the ICU standard of care procedures.

- Standard of care procedures include:
- Monitoring of O2/CO2 levels;
  - Avoiding hypotension;
  - Maintaining temperature within normative range;
  - Adjusting cervical collar placement if necessary;
  - Repeat CT scan if necessary;
  - Bed placement at > 30 degrees while in the ICU
  - Sedation and analgesia using recommended agents

If the subject is admitted to the ED Observation Unit, he/she will be treated according to the ED standard of care procedures.

The application of the Photomedex helmet will be in addition to but will not change the standard of care.

The following table summarizes the timing and specific assessments to be conducted in this study:

ASSESSMENTS	PRE-PROCEDURE	PROCEDURE	FOLLOW UP
Eligibility Assessment	X		
Informed Consent Form a	X		
Demographics, including date of birth, gender, and race and ethnicity	X		
Medical History	X		

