## **10. Adverse Events**

Adverse events will be reviewed by the Principal Investigator, Research Monitor and the DSMB and will be reported to the Human Research Committee within the required time frame and to all participating investigators according to the Partners Human Research Committee guidelines.

Underlying diseases or conditions are not reported as AEs unless there is an increase in severity or frequency during the course of the investigation. Death should not be recorded as an adverse event, but should only be reflected as an outcome to the applicable AE that led to the death.

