In order to review the data in an unblinded fashion, we will establish a DSMB of experienced specialists from Trauma, Neurology, Radiology, Rehabilitation at MGH and Spaulding, and the Wellman Center at MGH who are not conflicted or study staff members to review the safety data. The DSMB will review the data collected after the first 10 subjects have been enrolled. The DSMB will make a recommendation as to whether or not the study should continue. If the DSMB recommends continuation of the study, subsequent DSMB review of data once per year.

Additionally, [name] MD, a neurologist at MGH and member of the DSMB will serve as an independent research monitor for the study. He will review the research protocol with the

investigators, review the monitoring plan, and review study data. If the research monitor is concerned for the safety and well-being of the subjects he/she will have the authority to stop the research protocol in progress, remove individual human subjects from a research protocol, and take whatever steps are necessary to protect the safety and well-being of human subjects until the IRB can assess the monitor's assessment. The research monitor will review all unanticipated problems involving risk to subjects or others, device-related serious adverse events and all subject deaths associated with the protocol. At a minimum, the research monitor must comment on the outcomes of the event or problem and in case of a device-related serious adverse event or death, comment on the relationship to participation in the study. The research monitor must also indicate whether he/she concurs with the details of the report provided by the principal investigator. The research monitor will provide an unbiased written report Reports for events determined by either the investigator or research monitor to be possibly or definitely related to participation and reports of events resulting in death will be promptly forwarded to the USAMRMC ORP HRPO.

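### The adverse-event part of the primary endpoint counts only device-attributed events, and no all-cause safety comparison against sham is planned beside it

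*Protocol*

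**What the plan says.** The Synopsis defines the primary endpoint as the "number of subjects who successfully complete the study without adverse events significantly related to application of the device". It has two parts: completion, and absence of device-attributed events. The protocol does not define successful completion or how strong the relation to the device must be. It gives no causality scale and does not name the rater.

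Other passages bear on the point:

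- Protocol section 7 describes 1:1 allocation to active or sham, in 9 groups of 10. It sets a deterioration point at which the criterion for "withdrawing a subject will be a change in the GCS of greater than 2 from the previous exam".
- Section 10 says "Underlying diseases or conditions are not reported as AEs unless there is an increase in severity or frequency during the course of the investigation", so worsening of the brain injury is recordable. Death is recorded as an outcome of an event, not as an event. The principal investigator, the research monitor and the DSMB all review adverse events.
- Section 12.1 says "In order to review the data in an unblinded fashion, we will establish a DSMB", and that a "member of the DSMB will serve as an independent research monitor for the study". The monitor must, "in case of a device-related serious adverse event or death, comment on the relationship to participation in the study". For onward reporting, the same section uses a different relatedness threshold (possible or definite) and accepts either the investigator's or the monitor's view.
- The SAP covers baseline comparisons, a mixed model for the diffusion parameters and a similar model for clinical symptoms. It contains no adverse-event analysis.

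**The concern.** In acute brain injury, many of the harms one would look for after a transcranial intervention (seizure, bleed expansion, a fall in GCS, worse symptoms) also belong to the course of the injury. A clinician judging a single case has a ready alternative explanation and will often call the event unrelated. Randomisation against sham removes the need for that judgement: if the device does harm, events of every kind should be more frequent in the active arm. The primary endpoint filters events by attribution before the arms can be compared, and the SAP supplies no unfiltered comparison.

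At stake is the trial's primary conclusion. A high success count in both arms could be reported as evidence of safety while neurological worsening is more frequent on active treatment.

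The attribution step also has no stated protection. The documents do not require relatedness to be rated before allocation is seen, and one of the reviewers belongs to a board that works unblinded.

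**Working it through.** **The plan's own figure.** The only sample-size figure is 82 (41 per group) for fractional anisotropy, from an assumed 25% effect and a 40% CV. It reproduces: 16/(0.25/0.40)² = 40.96, or 41 per group, which corresponds to a two-sided 5% level and 80% power (neither is stated in section 9). It says nothing about the safety endpoint, for which there is no calculation.

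**Inputs.** From the protocol: 90 subjects at 1:1, so 45 per arm. The documents give no adverse-event, withdrawal or attribution rates, so the following are assumptions:

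- p, the true proportion with neurological worsening: 5% sham, 15% active;
- w, the share of worsening subjects who do not complete: 0 to 1;
- q, the share of the remaining worsening subjects whose event is called device-related: 0 to 0.20, equal in both arms.

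Other reasons for non-completion are left out.

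**Expected subjects with worsening.** 45 × 0.05 = 2.25 sham; 45 × 0.15 = 6.75 active.

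**Success as the endpoint counts it.** Success = 1 − p × [w + (1 − w) × q].

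| w | Sham, q = 0.20 to 0 | Active, q = 0.20 to 0 |
|---|---|---|
| 0 | 99% to 100% | 97% to 100% |
| 0.25 | 98% to 98.75% | 94% to 96.25% |
| 0.5 | 97% to 97.5% | 91% to 92.5% |
| 1 | 95% | 85% |

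Example for the active arm, w = 0.25, q = 0.20: 1 − 0.15 × (0.25 + 0.75 × 0.20) = 1 − 0.15 × 0.40 = 0.94.

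**Worsening subjects counted as successes.** 45 × p × (1 − w) × (1 − q). At w = 0.25, q = 0.20: 1.35 sham and 4.05 active. At w = 1: none.

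**A second scenario, higher rates.** Assume 20% sham and 40% active, all completing: 9 v 18 subjects, a 20-point difference. At 25% attribution in both arms the endpoint counts 2.25 v 4.5, a 5-point difference.

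**If attribution differed by arm.** Assume a true rate of 20% in both arms, with 25% attribution on active and none on sham: 45 × 0.20 × 0.25 = 2.25 counted on active and 0 on sham, with no real harm. This shows why blinding of the rating matters. It is not evidence that the bias occurs.

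**What an all-cause comparison can show.** At 5% v 15%, the standard error of the risk difference is √(0.05 × 0.95/45 + 0.15 × 0.85/45) = 0.062. The 95% interval is about 10 ± 12.2 points, or −2 to 22. Two-sided Fisher power at the 5% level is about 23%; at 20% v 40% it is about 46%.

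**The case against.** The strongest reply is that the endpoint has a second part. A subject must also be among the "number of subjects who successfully complete the study", and this needs no attribution. A GCS change of more than 2 is a withdrawal point, and a subject who dies does not complete, so severe worsening lowers the count. This stands. A reader might infer that all harm resembling the injury vanishes from the endpoint; the documents do not support that. The 97-100% figure is the extreme in which every worsening subject completes. Nor does a three-fold excess simply disappear: at w = 0, q = 0.20 the counted events are 0.45 v 1.35, still three-fold, and only q = 0 removes it.

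The completion part does not close the gap. The GCS trigger is measured against the previous examination, so a change of 2 or less, or stepwise changes of that size, does not meet it. A seizure or symptom worsening need not meet it either. Follow-up runs to a 12-month telephone call (section 7.3), so non-completion also includes ordinary loss to follow-up.

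The reply also notes that worsening is recordable as an adverse event, that the DSMB sees unblinded safety data, and that the SAP models clinical symptoms by arm without an attribution filter. All of this is true and protects subjects, but none of it puts an all-cause comparison of events into the planned analysis.

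A reader might also infer that an arm-aware monitor decides which events count. The documents do not show this. They do not say that the monitor's opinion settles the endpoint or that allocation is known when it is given. The monitor's stated comment on relationship is tied to device-related serious events and deaths, and for reporting the monitor cannot overrule a positive attribution by the investigator. What remains is narrower: the rater is unnamed and blinding of the rating is not required.

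**Conclusion.** The concern holds in a limited form. The adverse-event part of the primary endpoint depends on attribution, the sham arm is not used for an all-cause safety comparison, and the SAP does not make good the gap. Worsening attributed to the injury in a subject who still completes is counted as a success.

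The size depends on how many worsening subjects leave the trial. At an assumed 5% v 15% with 0-20% attribution, success in the active arm lies between 85% (none complete) and 97-100% (all complete), so the loss of information runs from nil to nearly complete. The rates, withdrawal shares and attribution shares are all assumptions.

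On blinding, the finding is a missing safeguard, not a demonstrated bias.

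**What to change.** Keep the existing endpoint and define its two terms: successful completion, and the degree of relatedness that counts. Beside it, report by arm, regardless of attribution, the number of subjects with any adverse event, any serious adverse event, any neurological worsening after first application, and withdrawal or death. Give risk differences with 95% confidence intervals, and base the safety conclusion on this comparison. List loss to follow-up separately from withdrawal for deterioration.

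Keep device-relatedness as a secondary classification, made by a named blinded assessor and recorded before any unblinded review.

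The cost is some wording and one table, since adverse events are already collected. There are three downsides. Background injury events will make the headline figure less favourable in both arms. With 45 per arm the comparison is descriptive and cannot establish the absence of harm. And because the SAP (dated 6.26.20) is written in the past tense, the table should be labelled as an addition to the plan rather than presented as prespecified.
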